#### **8.2.4. Pre-Discharge Assessments**

Prior to hospital discharge, the following assessments should be performed:

- **Cardiac medication and anticoagulation regimen** (only cardiac related AADs, anticoagulation regimen, etc.)
- **ECG** in case of standard of care
- **Endoscopy:** imaging of the esophagus for the detection of esophageal injury within 72 hours post-procedure; prior to discharge.
- **Transthoracic echocardiogram (TTE)** to assess the pericardium. In the event of a significant pericardial effusion is identified, subjects should be followed until the condition resolves.
- **Adverse events**, if any
- **Occurrence of AF or other arrhythmias**, if any
- **Cerebral MRI** (within 72hours post procedure), Neurological exam and Neurological Evaluation using the NIH stroke Scale (NIHSS) within 72- hours post procedure, prior to discharge. A certified/qualified physician expert must perform neurological exams.

### **8.2.5. Repeat Ablation Procedures**

Repeat ablation procedures and management of arrhythmia recurrences during follow-up may be performed at the discretion of the investigator. Repeat procedures during follow up may be managed per investigator discretion using a commercially approved and available ablation catheter. It's recommended to perform repeat ablations with the THERMOCOOL SMARTTOUCH® SF-5D system. The follow-up schedule will remain based on the initial ablation procedure.

## **8.3. Post-Ablation Follow-up Schedule**

The subject will be required to complete follow up visits through 3 months post initial ablation procedure. Follow-up will be done at 7 days (phone call or clinic visit), 1 month (if applicable) and 3 months (clinic visits).

Discharged subjects will receive a telephone call or have a clinic visit at 7 days (7D, day 6-8) post ablation procedure to assess cardiac medication AFL/AF/AT occurrences and occurrence of (Primary) Adverse Events.

The subject will be required to complete follow up through 3 months post initial ablation procedure. The follow-up visits are 1 month  $\pm$  7 days (1M, day 23-37) (if applicable) and 3 months  $\pm$  14 days (3M, day 76-104) post ablation procedure. Follow-up visit schedule should be based on the date of the index study ablation procedure and will not reset if subject undergoes a repeat AF ablation procedure.

- If findings of micro-emboli/neurologic deficits/ CVA or TIA events identified at a prior evaluation (i.e. pre-discharge) a 1 month follow up visit will be performed with the following assessment:
  - Cerebral MRI, Neurological Exam and NIH Stroke Scale (NIHSS), MoCA and mRS assessments. Subjects with findings of micro-emboli/neurologic deficits/CVA/TIA will undergo additional MoCA/mRS through 3M follow-up
- At the 3 months post ablation procedure visit (clinic visits) the following assessments should be performed:
  - Cardiac medication and anticoagulation regimen (only cardiac related AADs, anticoagulation regimen, etc.)
  - Medical / Hospitalization History
  - NYHA Functional Class Scale.
  - ECG in case of standard of care
  - Adverse events, if any
  - AFL/AT/AF occurrence and repeat ablation
  - Cerebral MRI, Neurological Exam and NIH Stroke Scale (NIHSS) and MoCA/mRS assessments will be performed in case observations findings of micro-emboli/neurologic deficits were noted during previous assessments. A certified/qualified physician must perform neurologic exams at pre-and post-ablation and possibly at other follow-up visits, pending findings of micro-emboli/neurological deficits.
  - End of Study Follow up

#### **8.4. Final Study Visit**

The Final Study visit for each participant will be conducted 3 months  $\pm$  14 days post ablation procedure.

#### **8.5. Early Termination Visit**

If early termination of the study is required due to safety concerns, each site will undergo a monitoring visit to conclude any outstanding issues, collect all outstanding CRF information, verify device accountability, and discuss any other items relevant to the conclusion of the study. Any enrolled subjects will continue to be followed per the study protocol requirements.

#### **8.6. Unscheduled visit**

If subject returns for a potential study related cardiovascular or neurological visit outside of the protocol-defined visit schedule provided in Table 4, the visit will be considered "unscheduled" (UNS). An investigator may request an unscheduled visit in the presence of a new or worsened cardiovascular condition or neurological deficit. If the unscheduled visit is for a repeat ablation procedure, the protocol follow-up schedule is based on the index ablation procedure. For all unscheduled visits, an unscheduled visit eCRF must be completed and the subject must also return for their next scheduled study visit per clinical investigational plan.

#### **8.7. Core Laboratory for Evaluation**

No core lab will be used during this study

## 8.8. Schedule of Events Table

This table displays the required schedule for subject treatments and evaluations

**Table 3 Summary of Subject Assessments**

Assessments	Pre-ablation	Pre-discharge	7D (D6-8)	M1 (D23-37)	M3 (D76-104)	UNS
Clinic visit	●			● 9/10	●	●
Phone Call			● 			
Patient Informed Consent  /Demographics	●					
Medical/AF history	●					
Cardiac Medication and anti-coagulation Regimen	●	●	●	● 	●	●
CHA2DS2-Vasc Score	●					
NYHA functional Class Scale	●				●	
Pregnancy Test	● 					
Transthoracic Echo (TTE)	● 	●				
LA thrombus detection	● 					
ECG	● 	● 			● 	● 
Adverse events	●	●	●		●	●
AFL/AT/AF occurrence and repeat ablation		●	●		●	●
Endoscopy		● 				
Cerebral MRI	● 	● 		● 	● 	● 
Neurological Exam	● 	● 		● 	● 	● 
NIH Stroke Scale	● 	● 		● 	● 	● 
mRS	● 			● 	● 	● 
MoCA	● 			● 	● 	● 

1. May be substituted with a clinic visit.
2. To be completed within 60 days prior to ablation procedure
3. In all women of childbearing age and potential. To be completed within 1 week prior to ablation procedure.
4. To be performed within 30 days prior to procedure to determine the LA size and LVEF%, if the subject has undergone an imaging procedure within the last 6 months where the atrial size was assessed, the pre-procedure imaging assessment is not required.
5. To be completed the day before or the day of the study ablation procedure. Imaging modality TEE, ICE, CT or MRI.
6. To be collected if completed as standard of care.
7. To be completed within 72-hours pre-procedure.
8. To be completed within 72-hours post-procedure.
9. To be undertaken/collected if neurologic symptoms and/or new cerebral ischemic lesions identified/CVA/TIA reported in a prior evaluation.
10. To be completed only if a previous mandated test was missed, or if subject reports neurologic difficulties between scheduled follow-up visits and unscheduled assessment per investigator approval

## 9. Assessment of Safety

### 9.1. Specific Safety Parameters

#### 9.1.1. *Definition of Adverse Events (AE)*

An AE is any untoward medical occurrence in a subject whether or not related to the investigational medical device.

Specifically, an adverse event (AE) is any undesirable experience (sign, symptom, illness, abnormal laboratory value, or other medical event) occurring to a subject during the course of the study, whether or not it is related to the device or procedure. Physical findings (including vital signs) observed at follow-up, or pre-existing physical findings that worsen compared to baseline, are considered adverse events.

Any medical condition that is present at the time that the participant is screened will be considered as baseline and not reported as an AE. Such conditions should be added to background medical history, if not previously reported. However, if the study participant's condition deteriorates at any time during the study, it will be recorded as an AE.

AF recurrence by itself is considered a recurrence of disease (pre-existing condition), and, therefore, does not meet the definition of an AE. Recurrence of pre-existing AFL/ atrial tachycardia (AT) is also considered recurrence of disease, and does not meet the definition of an AE.

The following clinical events will not be considered an adverse event for this clinical study:

- Minor pericarditis attributable to the ablation procedure defined as pleuritic chest discomfort with or without pericardial rub and ECG changes.
- AF/AFL/AT recurrence requiring pharmacological or synchronized electrical cardioversion during the hospitalization for the index ablation procedure, or throughout the duration of the study. However, new onset of left atrial flutter occurring post-ablation is an AE. Re-ablation for AF or preexisting AFL/AT itself is not an AE, however any procedural complication is considered an AE and shall be reported within the applicable timelines.

#### 9.1.2. *Definition of Serious Adverse Event (SAE)*

A serious adverse event (SAE) is ANY event that meets one or more of the following criteria:

- Leads to a death
- Leads to a serious deterioration in the health of a subject that resulted in:
  - A life-threatening illness or injury
  - An injury or permanent impairment of a body structure or a body function
  - In-patient hospitalization or prolongation of an existing hospitalization\*
  - Medical or surgical intervention to prevent life-threatening illness or injury or permanent impairment to body structure or a body function
- Leads to fetal distress, fetal death or a congenital abnormality or birth defect.

\*Planned hospitalization for a condition present prior to the participant's enrollment in the study will not meet the definition of an SAE. An AE would meet the criterion of "hospitalization" if the event necessitated an admission to a health care facility (e.g., an overnight stay). Emergency room (ER) visits that do not result in admission to the hospital should be evaluated for one of the other serious outcomes.

### 9.1.3. Primary Adverse Event (PAE)

A Primary AEs is an event listed in Table 4 which occurs within the first week (7 days) following an ablation procedure. Primary AEs are considered SAEs.

**Table 4 Primary Adverse Events**

Primary Adverse Event	Description / Criteria
Atrio-Esophageal Fistula*	Defined as a connection between the atrium and the lumen of the esophagus. Evidence supporting this diagnosis includes documentation of esophagus erosion combined with evidence of a fistulous connection to the atrium such as air emboli, an embolic event, or direct observation at the time of surgical repair. A CT or MRI scan is the most common method of documentation of an atrio-esophageal fistula.
Cardiac Tamponade**/Perforation	
The development of a significant pericardial effusion during or within 30 days of undergoing the index AF ablation procedure. A significant pericardial effusion is one that results in hemodynamic compromise, requires elective or urgent pericardiocentesis, or results in a 1cm or more pericardial effusion as documented by echocardiography
 
Cardiac tamponade/perforation should also be classified as:
 
Early – diagnosed prior to discharge
 
Late – following initial discharge from the hospital

Death*	Subject death directly related to the device or procedure and occurs at any time during or after the procedure.
Major Vascular Access Complication /Bleeding	
Major Bleeding:
 
Requires and/or treated with transfusion or results in a 20% or greater fall in hematocrit.
 
Major Vascular Access Complication:
 
Defined as a hematoma, an AV fistula or a pseudoaneurysm which requires intervention such as surgical repair or transfusion, prolongs the hospital stay, or requires hospital admission.

Myocardial Infarction	
Presence of any one of the following criteria:
 

– Detection of ECG changes indicative of new ischemia (new ST-T changes or new left bundle branch block [LBBB]) that persist for more than 1 hour

– Development of new pathological Q waves on ECG

– Imaging evidence of new loss of viable myocardium or new regional wall motion abnormality

Phrenic Nerve Paralysis	Absent phrenic nerve function as assessed by a sniff test, and associated with symptoms of dyspnea and orthopnea (diagnosed by chest x-ray). A phrenic nerve paralysis is considered to be permanent when it is documented to be present 12 months or longer following ablation. Under this protocol, diaphragmatic paralysis/phrenic nerve palsy will be considered a Primary AE if specified symptoms have not improved at the 3-month final visit

Primary Adverse Event	Description / Criteria
Pulmonary Vein Stenosis*	
A reduction of the diameter of a PV.
 
Severe PV stenosis (<math>\geq 70\%</math> reduction in the diameter of the PV) will be considered a primary adverse event and major complication of AF ablation.

Stroke/Cerebrovascular Accident (CVA)	
Diagnosis:
 
 
-Rapid onset of a focal or global neurological deficit with at least one of the following: change in level of consciousness, hemiplegia, hemiparesis, numbness or sensory loss affecting one side of the body, dysphasia or aphasia, hemianopia, amaurosis fugax, or other neurological signs or symptoms consistent with stroke.
 
-Duration of a focal or global neurological deficit <math>\geq 24</math> h; or <math><24</math> h, if therapeutic intervention(s) were performed (e.g. thrombolytic therapy or intracranial angioplasty); OR available neuroimaging documents a new hemorrhage or infarct; or the neurological deficit results in death.
 
-No other readily identifiable non-stroke cause for the clinical presentation (e.g., brain tumor, trauma, infection, hypoglycemia, peripheral lesion, pharmacological influences).†
 
-Confirmation of the diagnosis by at least one of the following: Neurology or neurosurgical specialist; Neuroimaging procedure (MR or CT scan or cerebral angiography); Lumbar puncture (i.e., spinal fluid analysis diagnostic of intracranial hemorrhage)
 
 
Definition:
 
Stroke: (diagnosis as above, preferably with positive neuroimaging study)
 
 
Minor—Modified Rankin score <math><2</math> at 30 and 90 days††
 
Major—Modified Rankin score <math>\geq 2</math> at 30 and 90 days
 

Transient Ischemic Attack	New focal neurological deficit with rapid symptom resolution (usually 1 to 2 h), always within 24h; neuroimaging without tissue injury.
Thromboembolism	Formation of a clot (thrombus) inside a blood vessel causing obstruction to blood flow. The thrombus can migrate (embolus) and obstruct distal vascular sites. Diagnostic tests to help detect thromboembolisms may include but are not limited to angiography (pulmonary or distal), ventilation-perfusion (V/Q) scans, venography, Doppler ultrasonography, spiral CT, and echocardiography.

\* Device or procedure related death, atrio-esophageal fistula and pulmonary vein stenosis that occur greater than one week (7 days) post-procedure shall be deemed Primary AE.

\*\* Hemodynamic compromise or instability is defined as Systolic blood pressure  $< 80$  mmHg

† Patients with non-focal global encephalopathy will not be reported as a stroke without unequivocal evidence based upon neuroimaging studies.

†† mRS assessments should be made by qualified individuals according to a certification process. If there is discordance between the 30 and 90 day mRS, a final determination of major versus minor stroke will be adjudicated by an independent physician/committee.

#### **9.1.4. Adverse Device Effect (ADE) / Serious Adverse Device Effect (SADE)**

An Adverse Device Effect (ADE) is an adverse event related to the use of the investigational medical device.

**NOTE 1:** This includes any adverse event resulting from insufficiencies or inadequacies in the instructions for use, the deployment, the implantation, the installation, the operation, or any malfunction of the investigational medical device.

**NOTE 2:** This includes any event that is a result of a use error or intentional abnormal use of the investigational medical device.

A Serious Adverse Device Effects (SADE) is an adverse device effect that has resulted in any of the consequences characteristic of an SAE.

#### **9.1.5. Unanticipated (Serious) Adverse Device Effect (UADE/USADE)**

An unanticipated adverse device effect (UADE) or unanticipated serious adverse device effect (USADE) is any serious adverse effect on health, safety, any life-threatening problem, or death caused by, or associated with a device, if that effect, problem, or death was not previously identified in nature, severity, or degree of incidence in the investigational plan or risk analysis report, or any other unanticipated serious problem associated with a device that relates to rights, safety, or welfare of subjects.

Refer to Table 8 for a comprehensive list of foreseeable and anticipated adverse events.

#### **9.1.6. Study Device Deficiency, Failure or Malfunction**

A device has failed if it does not perform according to the IFU or fails to meet the expectations of the device and/or investigator (i.e., related to appearance of the device, performance, durability, safety, effectiveness, quality, reliability, labeling, etc.). If a device failure is detected or suspected, it should be documented on the appropriate eCRF and device failure and AE must be reported as soon as possible to the Sponsor per section 9.4.

### **9.2. Classification of an Adverse Event**

#### **9.2.1. Severity of Event**

The intensity or severity of each AE must be assessed according to the following classifications:

**Table 5 Intensity or Severity Definitions**

Mild	Awareness of signs, symptoms, or events that are otherwise easily tolerated that may result in minimal transient impairment of a body function or damage to a body structure, but do not require intervention other than monitoring.
Moderate	Any event that results in moderate transient impairment of a body function or damage to a body structure that causes interference with usual activities, or that warrants possible intervention, such as the administration of medication, to prevent permanent impairment of a body function or damage to a body structure.
Severe	Any event that is incapacitating (an inability to do usual activities) or is life-threatening and results in permanent impairment of a body function or damage to a body structure, or requires intervention, such as major surgery, to prevent permanent impairment of a body function or damage to a body structure.

### 9.2.2. *Relationship to Study Device*

For all collected AEs, the clinician who examines and evaluates the participant will determine the AE's causality based on temporal relationship and his/her clinical judgment. The degree of certainty about causality will be graded using the categories below, based on MEDDEV 2.7/3 Rev.3.

**Table 6 Adverse Event Causality Classifications**

Caused By	Relationship	Definition of Relation
Device	Causal	The event is associated with the investigational device beyond reasonable doubt
	Probable	The relationship with the use of the investigational device seems relevant and/or the event cannot reasonably explained by another cause, but additional information may be obtained
	Possibly	The relationship with the use of the investigational device is weak but cannot be ruled out completely
	Unlikely	The relationship with the use of the investigational device seems not relevant and/or the event can be reasonably explained by another cause, but additional information may be obtained
	Not Related	Relationship to the investigational device can be excluded
Study Procedure	Causal	The event is associated with the study procedure beyond reasonable doubt
	Probable	The relationship with the study procedure seems relevant and/or the event cannot be reasonably explained by another cause, but additional information may be obtained
	Possibly	The relationship with the study procedure is weak but cannot be ruled out completely
	Unlikely	The relationship to the study procedure seems not relevant and/or the event can be reasonably explained by another cause, but additional information may be obtained
	Not Related	Relationship to the procedure can be excluded

### 9.2.3. *Outcome*

The outcome of each AE must be assessed according to the following classifications:

**Table 7 Adverse Event Outcome Classifications**

Classification		Definition
Recovered	Resolved	Subject fully recovered with no observable residual effects
	Resolved with sequelae	Subject recovered with observable residual effects
Recovering	Resolving	Adverse event has not resolved and additional change in condition is possible
Not Recovered	Not Resolved	Subject didn't recover from the AE and the observed AE effects are still present
Fatal		Subject died as a result of the AE (whether or not the AE is related to the device or procedure)

#### 9.2.4. **Expectedness**

An anticipated Adverse Event is an effect which by nature, incidence, severity or outcome has been identified as a possible complication associated with the investigational medical device and/or intervention procedure.

Potential adverse events that are reasonably anticipated to occur during the cardiac electrophysiology procedure are listed in Table 8. These events should be reported via EDC as anticipated AEs. Anticipated adverse events are to be reported to the sponsor via EDC as indicated in section 9.4.

**Table 8 A provides a comprehensive list of anticipated AEs.**

Anticipated Adverse Events	
Acute Respiratory Distress Syndrome (ARDS)	Air embolism
Allergic reaction	Allergic reaction to Anesthesia (e.g., hair loss)
Anaphylactic shock	Anemia
Anesthesia reaction	Apnea - sedation induced
Arrhythmia: bradycardia	Arrhythmia: pro-arrhythmias
Arrhythmia: tachycardia	Aspiration pneumonia
Asthmatic attack	Atelectasis
Atelectasis	Atrial fibrillation*
Atrio-Esophageal fistula	Atypical left atrial flutter
AV fistula	Bleeding complications
Bleeding requiring transfusion	Cardiac arrest
Cardiac perforation	Cardiac thrombo-embolism
Cerebro-vascular accident (CVA) / stroke	Chest pain/discomfort
Complete heart block, temporary or permanent	Conduction block: ongoing / resolved
Congestive Heart Failure	Coronary artery dissection
Coronary artery occlusion	Coronary artery spasm
Coronary artery Thrombosis	Damage to the vascular system
Death	Deep venous thrombosis
Diaphragmatic paralysis	Dislodgement of permanent pacing leads
Disseminated Intravascular Coagulation	Dyspnoea
Endocarditis	Epistaxis
Esophageal Injury	Exacerbation of pre-existing arrhythmia*
Expressive aphasia	Fainting
Fatigue	Gastric reflux
Gastrointestinal diverticulosis	Gastro-intestinal NOS
Heart Failure	Hematoma (local) / ecchymosis
Hemorrhage	Hemothorax
High / increased creatine phosphokinase (CPK)	Hypotension
Hypoxia	Increase in frequency or duration of episodes of typical atrial flutter
Increased phosphokinase level	Infection, localized

Infection, systemic	Injury to skin, muscle, connective tissue due to body position, electrical cardioversion, etc.
Laceration	Leakage of air or blood into the lungs or other organs due to perforation
Liver toxicity	Mobile strands in Inferior Vena Cava
Myocardial infarction	Nausea
Neurological disorders (headache)	Neurological disorders (poor coordination)
Neurological disorders (tremor)	Obstruction to the vascular system
Palpitations	Perforation to the vascular system
Pericardial effusion without tamponade	Pericardial effusion resulting in tamponade
Peripheral embolus	Pericarditis
Peripheral thromboembolism	Peripheral nerve injury
Phrenic nerve damage	Phlebitis
Pneumothorax	Pleural effusion
Pulmonary edema	Pseudoaneurysm
Pulmonary hypertension	Pulmonary embolism
Pulmonary vein dissection	Pulmonary toxicity, like acute pulmonary syndrome
Pulmonary vein thrombus	Pulmonary vein Stenosis
Renal failure	Pump failure
Respiratory failure	Respiratory depression
Rhabdomyolysis, including produced by body position or propofol	Retroperitoneal hematoma
Seizure	Sedation induced CO 2 retention with lethargy and cholecystitis
Skin burns (due to cardioversion, tape, etc)	Sepsis
Skin injury / muscle or connective tissue injury due to body position, electrical cardioversion	Skin discoloration
Tamponade	Skin rash
Thrombocytopenia	Temperature elevation
Thrombosis	Thromboembolism
Transient extremity numbness	Thyroid disorders
Unintended complete or incomplete AV, Sinus node, or other heart block or damage	Transient ischemic attack (TIA)
Urinary tract injury or infection related to the urinary catheter	Urinary retention
Vasovagal reactions	Valvular damage/insufficiency
Volume overload	Vision change
X-ray radiation injury of skin, muscle and/or organ	Worsening obstructive, restrictive, or other form of pulmonary disease

\*Atrial Fibrillation and exacerbation of an existing arrhythmia are anticipated adverse events. However, they will not be captured as such under this protocol, as they are considered recurrence of disease.

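### The protocol gives conflicting rules on whether worsening of a pre-existing arrhythmia is an adverse event, so it can be left out of the secondary SAE, SADE and non-serious AE counts

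*Protocol*

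**What the plan says.** Protocol section 9.1.1 treats a condition present at screening as baseline and then adds: "However, if the study participant's condition deteriorates at any time during the study, it will be recorded as an AE". It also says that "pre-existing physical findings that worsen compared to baseline, are considered adverse events".

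The same section then takes certain arrhythmia events out of the definition:

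- AF: "AF recurrence by itself is considered a recurrence of disease (pre-existing condition), and, therefore, does not meet the definition of an AE".
- Flutter and atrial tachycardia: "Recurrence of pre-existing AFL/ atrial tachycardia (AT) is also considered recurrence of disease, and does not meet the definition of an AE".
- Also listed as not an AE: "AF/AFL/AT recurrence requiring pharmacological or synchronized electrical cardioversion during the hospitalization for the index ablation procedure, or throughout the duration of the study".
- Re-ablation for AF or pre-existing AFL/AT is not in itself an AE, although a complication of it is.
- New-onset left atrial flutter after ablation stays an AE.

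Section 9.2.4 tells sites to report the events in Table 8 as anticipated AEs. In that table the rows for AF and for exacerbation of a pre-existing arrhythmia carry an asterisk. The footnote names AF first, then says: "exacerbation of an existing arrhythmia are anticipated adverse events. However, they will not be captured as such under this protocol, as they are considered recurrence". The row "Increase in frequency or duration of episodes of typical atrial flutter" carries no asterisk. Neither do the rows for pro-arrhythmias, tachycardia and atypical left atrial flutter.

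Section 9.1.2 defines an SAE as any event that meets a seriousness criterion and makes no exception for arrhythmia. SAP section 10.4 counts SADEs, SAEs and non-serious AEs, by event and by subject, over three months. It gives no rule for worsening of an arrhythmia.

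**The concern.** Recurrence means that the treatment has not abolished the arrhythmia. Exacerbation means that the subject is worse than before treatment. The first is a question of effectiveness. The second may be an effect of the device or procedure, and section 9.2.4 itself describes anticipated events as possible complications of these. The footnote puts the second under the first.

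The consequence passes down the definitions. Under section 9.1.4 an adverse device effect is a kind of AE, and a SADE is a serious one. An event that is never recorded as an AE therefore does not reach the SAE, SADE or non-serious AE endpoints. It also misses the 72-hour reporting in Table 9 and the sponsor's review of seriousness and relatedness in section 9.4.1. Section 1.2.2 describes this study as the first experience with the catheter and generator including TGA mode, and these counts are part of what it is meant to provide. With up to 10 centers, sites may well follow different sentences.

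**Working it through.** The plan states no figure on this point, so the main check sets the passages side by side.

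**1. One record under each passage.** Take a subject with typical flutter at baseline who, at week 3, has longer and more frequent episodes and is admitted to hospital.

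| Passage | Classification |
|---|---|
| 9.1.1, deterioration rule | AE |
| 9.1.2, hospitalization criterion | SAE, if the event is an AE at all |
| 9.2.4 with the unstarred flutter row of Table 8 | Reportable as an anticipated AE |
| Table 8 footnote, exacerbation | Not captured |
| 9.1.1, cardioversion exemption | Not an AE, if the admission was for cardioversion and the episode is read as recurrence |

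The last row matters. Section 9.1.1 already exempts some recurrences that need intervention, so the record is not an SAE on every reading of that section.

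**2. Can the footnote be read as a restatement of 9.1.1?** The exemptions in 9.1.1 name recurrence and re-ablation; none names worsening. The footnote names exacerbation and gives recurrence of disease as the reason. That is the ground on which 9.1.1 puts an event outside the AE definition, so the natural reading is that exacerbation is not recorded as an AE. This is wider than 9.1.1 and contradicts its deterioration rule. It also contradicts Table 8 itself, because more frequent or longer flutter in a subject with prior flutter is an exacerbation, and that row has no asterisk.

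**3. What is not affected.** No arrhythmia appears among the Primary Adverse Events in Table 4, so the primary safety endpoint does not change. New pro-arrhythmia and new-onset left atrial flutter remain reportable.

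**4. Scale.** Assume that all 50 planned subjects are in the Safety Population.

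- Shift per affected subject: at most 1/50 = 2.0 percentage points. The shift is zero if that subject already has another event in the same category.
- If 2% to 10% of subjects worsened (an assumption; the documents give no rate), that is 0.02 × 50 = 1 to 0.10 × 50 = 5 subjects, and a shift of at most 2 to 10 points.
- Chance of at least one such subject, 1 − (1 − p)^50: 39.5% for p = 1%, 63.6% for 2%, 92.3% for 5% and 99.5% for 10% (all assumed rates).
- In a category with no other events, one omitted subject is the difference between 0/50 (exact two-sided 95% interval 0% to 7.11%) and 1/50 = 2.0% (0.05% to 10.65%).

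**The case against.** The strongest reply is that the specific governs the general: the deterioration rule in 9.1.1 yields to the arrhythmia exemptions that follow it, and the footnote only restates these loosely. The words limiting the exemption to recurrence by itself stand only in the AF sentence; the flutter and atrial tachycardia sentence is unqualified. Recurrence needing cardioversion is exempt throughout the study, and re-ablation is not in itself an AE. This stands in part. It shows that 9.1.1 is generous and that some admissions are exempt without the footnote. It does not turn worsening into recurrence, and it does not explain the unstarred flutter row.

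A reader might infer that pro-arrhythmia in general is hidden, or that a serious worsening must be left out of the SAE count. The documents support neither. New arrhythmias stay reportable, and the any-event wording of 9.1.2 supports counting a serious worsening.

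It can also be said that the data are not lost. Table 3 collects AFL/AT/AF occurrence and repeat ablation before discharge, at 7 days, at 3 months and at unscheduled visits, and section 8.3 takes hospitalization history at 3 months. That is correct, but no listed endpoint or SAP analysis uses the arrhythmia occurrence data, and the footnote covers any existing arrhythmia, not only these three.

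Finally, the study is a descriptive feasibility study with no hypothesis test. That limits the consequence to the accuracy of reported incidences, but those incidences are its secondary safety results.

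**Conclusion.** The conflict is real but narrow. It concerns worsening of an arrhythmia that the subject already had. For that event the deterioration rule in 9.1.1 and the unstarred flutter row point to recording an AE, and the footnote points to recording nothing. Because the footnote makes no exception for seriousness or relatedness, it permits a serious or device-related worsening to be left out of the secondary SAE, SADE and non-serious AE counts; the text as a whole does not require this.

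The size is at most 2.0 percentage points per affected subject. This rests on 50 subjects in the Safety Population and on that subject having no other event in the same category. It would be wrong to read it as 2 points for every omitted event. How many subjects would be affected cannot be derived from the documents, and the typical-flutter conflict applies only to those who have that arrhythmia. The point is worth correcting because the counts can depend on which sentence a site follows and the correction is small.

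**What to change.** Reconcile the passages as follows.

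1. In the Table 8 footnote, delete exacerbation of an existing arrhythmia from the sentence on what is not captured, and remove the asterisk from that row. The footnote then covers only recurrence as exempted in 9.1.1 and agrees with the unstarred typical-flutter row.
2. In 9.1.1, state that worsening which the investigator judges to be beyond the subject's documented baseline arrhythmia is recorded as an AE, and as an SAE or SADE when 9.1.2 or 9.1.4 is met.
3. In the same place, state how this rule relates to the existing exemptions for recurrence needing cardioversion and for re-ablation.
4. Apply the same rule in SAP section 10.4.

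The cost is a few sentences. AF history at baseline and AFL/AT/AF occurrence at follow-up are already collected. There are two downsides. Reported AE and SAE incidence may be slightly higher. Judging worsening will also rest on the investigator, because the schedule contains no continuous rhythm monitoring and follow-up ECGs are collected only when done as standard of care; some variation between sites will remain.
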